3.4.3 Pharmacokinetic Variables

Pharmacokinetic endpoints include observed plasma concentrations and estimated PK parameters for nanatinostat and ganciclovir, and these will be described in a separate analysis plan.

3.4.4 Pharmacodynamic Variables

Pharmacodynamic endpoints include selected biomarkers of nanatinostat and valganciclovir activity with or without pembrolizumab (e.g., plasma EBV DNA levels), and these will be described in a separate analysis plan.

3.5 Data Quality Assurance

Report summaries will be generated using validated Base SAS® software, version 9.4 or higher, on a PC or server-based platform. Additional validated software may be used to generate analyses, as needed.

All SAS programs that create outputs or supporting analysis datasets will be validated by a second statistical programmer or biostatistician. At a minimum, validation of programs will consist of a review of the program log, review of output or dataset format and structure, and independent confirmatory programming to verify output results or dataset content. Additionally, all outputs will undergo a review by a senior level team member before finalization.

The content of the source data will be reviewed on an ongoing basis by project statistical programmers and statisticians. Data will be checked for missing values, invalid records, and extreme outliers through defensive programming applications, analysis-based edit checks, and other programmatic testing procedures. All findings will be forwarded to the project data manager for appropriate action and resolution.

4. STATISTICAL METHODS

4.1 General Methodology

Data will be analyzed by Emanate biostatistics personnel. Statistical analyses will be reported with tables, figures, and listings, presented in rich text format, and using recommended ICH numbering. Output specifications for all tables, figures, and listings will be in conformance with guidelines specified by the ICH in Appendix 7 of the Electronic Common Technical Document Specification ([Apr 2003](#)).

4.1.1 Reporting Conventions

The Phase 1b and Phase 2 portions of the study will be analyzed separately. Tables and figures will be summarized by dosing regimen. In general, all data collected, and any derived data will be presented in patient data listings, for all enrolled patients. Listings will be ordered by phase, site, patient number, treatment regimen, and assessment or event date. The dosing regimen presented in listings will be based on the planned assignment, unless otherwise noted.

In general, continuous variables will be summarized to indicate the study population sample size (N), number of patients with available data (n), mean, SD, median, first (Q1) and third (Q3) quartiles, minimum, and maximum values. Categorical variables will be summarized by the population size (N), number of patients with available data (n), number of patients in each category, and the percentage of patients in each category. Unless otherwise noted, and in order to determine the percentage of patients in each category, the denominator will be based on the number of patients with available data.

Select ordinal data may be summarized using both descriptive statistics and counts and percentages of patients in each category, as appropriate.

Non-zero percentages will be rounded to one decimal place. Rounding conventions for presentation of summary statistics will be based on the precision of the variable of summarization, as it is collected in its rawest form (i.e., on the electronic case report form [eCRF] or as provided within an external file) and are outlined as follows:

- The mean and median will be rounded to one more decimal place than the precision of the variable of summarization;
- Measures of variability (e.g., standard deviation, standard error) will be rounded to two more decimal places than the precision of the variable of summarization; and
- Minimum and maximum values will be presented using the same precision as the variable of summarization.

Other statistics (e.g., CIs) will be presented using the same general rules outlined above or assessed for the most appropriate presentation based on the underlying data.

No formal statistical analysis will be performed to compare treatment regimens. This study is exploratory in nature; descriptive statistics will be tabulated by treatment regimen and reviewed to evaluate all study endpoints.

4.1.2 Summarization by Visit

Data summarized by study visit will be based on the nominal, scheduled visit label as reported on the eCRF. Data collected for the last patient visit completed will be summarized separately, and this summary will be labeled as “End of Treatment.”

Data collected at unscheduled visits will not be included in by-visit summaries but will be considered when endpoint derivations potentially include multiple visits (e.g., determination of baseline value, determination of worst post-baseline value, etc.). All data will be included in patient listings.

4.1.3 Data Handling Rules

Unless otherwise noted, values reported as greater than or less than some quantifiable limit (e.g., “< 1.0”) will be summarized with the sign suppressed in summary tables and figures, using the numeric value reported. Data will display on patient listings to include the sign.

4.1.4 Baseline Value

Unless otherwise noted, the baseline value will be defined as the last value reported prior to first dose of any study drug.

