- p. **12-Lead ECG** All ECGs will be performed in triplicate. Average corrected QT interval using Fridericia's method (QTcF) is to be calculated to confirm eligibility. ECGs will be performed in triplicate as follows: 2 ECGs will be performed in triplicate pre-dose within 1 hour of dosing at least 15 minutes apart. For Phase 1b (dose levels 1-7), post-dose ECGs will be performed prior to and as close as possible to PK blood draws at 1-, 2-, 4-, and 6-hours post-dose (±15 minutes) on Cycle 1 Day 1. For Phase 1b (dose levels 8-13) and Phase 2, one set of triplicate ECGs will be performed on Cycle 1 Day 1 at 2 hours post-dose and on Cycle 2 Day 1 prior to and as close as possible to the PK blood draws at 1-, 2-, 3-, 4-(pre-dose of second divided dose), 5-, and 6-hours post-dose (±15 minutes). Detailed instruction on ECGs is provided in Section 7.4.2.5.
- q. For patients in Phase 2 who are receiving nanatinostat, valganciclovir, and pembrolizumab, all AEs will be collected for up to and including 90 days after the last dose of study treatment or until the start of a new antineoplastic therapy, whichever is first; for all other patients, only serious adverse events (SAEs) will be collected during this safety follow-up time period.
- r. **EBV DNA**, **CMV**, **HIV levels** Plasma samples will be collected to investigate circulating EBV DNA, CMV, and HIV (HIV⁺ patients only). EBV DNA levels will be utilized for safety and biomarker analysis. For patients in Follow-up: If no relapse/disease progression, then patients will continue to have EBV DNA levels monitored every 12 weeks for up to 1 year from the date of the last dose of study drug during the follow-up period, until disease progression, start of new anti-cancer treatment, or end of study, whichever occurs first.

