7.4.2.5. Cardiac Assessments: Electrocardiograms (ECGs)

All 12-lead ECGs will be conducted in triplicate. Average QTcF will be calculated to confirm eligibility. ECG tracings will be provided to a central laboratory, instructions are provided in the Study Manual.

Triplicate 12-lead ECGs will be performed separated by approximately 1 minute at screening, on Cycle 1 Day 1 (Phase 1b, all dose levels, and Phase 2), Cycle 2 Day 1 (Phase 1b dose levels 8 through 13 and Phase 2 only) and at the EOT visit. Average QTcF will be calculated to confirm eligibility. Careful skin preparation is essential to assure high quality ECGs. All ECGs should be collected using the same ECG machines and performed in as calm an environment as possible, not immediately following stressful procedures (ie, biopsies, etc.), with minimal distractions (talking, TV, etc.). Prior to each ECG, the patient should lie in a supine position in a calm environment for at least 5 minutes.

When performed in concert with serial PK collection on Cycle 1, Day 1 for Phase 1b dose levels 1 through 7, 2 ECGs will be performed pre-dose (within 1 hour of dose, separated by at least 15 minutes). Post-dose ECGs will be performed prior to and as close as possible to each PK sample collection at approximately maximum plasma concentration (maximum plasma concentration $[C_{max}]$; 1 and 2 hours), 4 hours, and 6 hours. If possible, patients should not consume additional food between dosing and the last ECG time point.

One set of triplicate 12-lead ECGs will be performed on Cycle 1, Day 1 at 2-hours post-dose for Phase 1b dose levels 8 through 13 and Phase 2. When performed in concert with serial PK collection on Cycle 2 Day 1 for these patients, 2 ECGs will be performed pre-dose (within 1 hour of dose, separated by at least 15 minutes). Post-dose ECGs will be performed prior to and as close as possible to each PK sample collection at approximately maximum plasma concentration (C_{max}; 1 and 2 hours), 3 hours, 4 hours, 5 hours, and 6 hours.

At screening and at the EOT visit, the ECG may be performed at any time during the clinic visit. ECGs may also be performed when clinically indicated, irrespective of the time of study drug dosing.

All ECGs will be independently reviewed by a central laboratory. Instructions for the collection and transmission of ECGs to the central ECG laboratory will be provided in the Study Manual.

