3.4.2.3 Other Safety Variables

All 12-lead ECGs will be conducted in triplicate. Triplicate 12-lead ECGs will be performed separated by approximately 1 minute at screening, on Cycle 1 Day 1 (Phase 1b, all dose levels, and Phase 2), Cycle 2 Day 1 (Phase 1b dose levels 8 through 13 and Phase 2 only) and at the EOT visit. Prior to each ECG, the patient will lie in a supine position in a calm environment for at least 5 minutes.

When performed in concert with serial PK collection on Cycle 1 Day 1 (for Phase 1b dose levels 1 through 7), two ECGs will be performed pre-dose (within 1 hour of dose, separated by at least 15 minutes). Post-dose ECGs will be performed prior to and as close as possible to each PK sample collection at approximately maximum plasma concentration (1 and 2 hours), 4 hours, and 6 hours.

When performed in concert with serial PK collection on Cycle 1 Day 1 (for Phase 1b dose levels 8 through 13 and Phase 2), two ECGs will be performed pre-dose (within 1 hour of dose, separated by at least 15 minutes) and one set of triplicate 12-lead ECGs will be performed on Cycle 1 Day 1 at 2-hours post-dose. When performed in concert with serial PK collection on Cycle 2 Day 1 for these patients, two ECGs will be performed pre-dose (within 1 hour of dose, separated by at least 15 minutes). Post-dose ECGs will be performed prior to and as close as possible to each PK sample collection at approximately maximum plasma concentration (1 and 2 hours), 3 hours, 4 hours, 5 hours, and 6 hours.

At screening and at the EOT visit, the ECG may be performed at any time during the clinic visit. ECGs may also be performed when clinically indicated, irrespective of the time of study drug dosing.

Vital signs (temperature, blood pressure, and heart rate) will be collected at the screening visit (Day -28 to Day -1), on Day 1 of each cycle, and at the EOT visit. On visit days requiring serial PK collection, vital signs will be collected just prior to the first dose of valganciclovir and nanatinostat, and in concert and just prior to PK blood draws. On other indicated visit days, vital signs will be collected once (prior to dosing of study treatment if administered in clinic).

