4.6.5 Vital Signs, Physical Findings, and Other Observations Related to Safety

4.6.5.1 Vital Signs

Descriptive statistics for vital sign parameter measurements will be presented for results and change from baseline at each visit where parameters were scheduled to be collected.

4.6.5.2 12-Lead Electrocardiogram

Descriptive statistics will be presented for observed values and changes from baseline at each visit where parameters were scheduled to be collected. All 12-lead ECGs will be conducted in triplicate. The average of the triplicate ECG interval parameters will be summarized by treatment regimen.

Twelve-lead ECGs will be classified by the investigator as “normal,” “abnormal, not clinically significant,” or “abnormal, clinically significant.” The worst classification for each set of triplicate 12-lead ECGs will be used for analysis. Three-by-three contingency tables will be presented to summarize the shift from the baseline category to the worst post-baseline value. Summary results will include the count and percentage of patients within each shift category and treatment group.

Prolonged QTc intervals will be summarized as QTc measurements (msec) that are >450, >480, and >500 msec averaged over each set of triplicate 12-lead ECGs at each visit where ECG is routinely collected per the clinical study protocol. Change from baseline categories will also be summarized for measurements that represent a change >30 or >60 msec relative to the baseline value. Summary results will include the percentage of patients within each category and treatment group.

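### For dose levels 1-7 the SAP's ECG baseline uses only the later of two pre-dose triplicate sets, so QTc change from baseline is slightly noisier than the collected data allow

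*SAP*

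**What the plan says.** **Baseline rule.** Unless an exception is noted, SAP 4.1.4 states that "the baseline value will be defined as the last value reported prior to first dose of any study drug".

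**ECG analysis.** SAP 4.6.5.2 notes no ECG exception. QTc is "averaged over each set of triplicate 12-lead ECGs at each visit", which is averaging inside one set. Nothing says how two sets before the same dose combine. The same section tabulates "a change >30 or >60 msec relative to the baseline value", alongside absolute categories above 450, 480 and 500 msec.

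**ECG collection.**
- SAP 3.4.2.3: "All 12-lead ECGs will be conducted in triplicate".
- Footnote p of the protocol's Table 11: "2 ECGs will be performed in triplicate pre-dose within 1 hour of dosing at least 15 minutes apart".
- Protocol 7.4.2.5 and SAP 3.4.2.3 both place this pair on Cycle 1 Day 1 for dose levels 1-7.
- For dose levels 8-13 and Phase 2 the two documents differ. SAP 3.4.2.3 again places the pair on Cycle 1 Day 1: "two ECGs will be performed pre-dose (within 1 hour of dose, separated by at least 15 minutes"). Protocol 7.4.2.5 says of that day only that "One set of triplicate 12-lead ECGs will be performed on Cycle 1, Day 1 at 2-hours post-dose", and puts the two pre-dose sets for these patients on Cycle 2 Day 1. Footnote p does not name the day of the pair for these levels.

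**The concern.** Two triplicate sets give up to six tracings before the first dose at dose levels 1-7. Under the general baseline rule only the later set counts, so every change value carries the full error of that one set, and so does every assignment to the above-30 category. Because all changes within a patient share one baseline, an unusually low baseline set can push several post-dose sets over the limit together.

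Protocol 1.6.2 lists QTc prolongation among the toxicities reported for other HDAC inhibitors. SAP 4.8 records that enrollment ended after Phase 1b, so these small cohorts are all the ECG evidence the study will have. In a regimen of 6 or 3 patients, one misclassified patient moves the tabulated percentage by 1/6 = 17 points or 1/3 = 33 points.

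**Working it through.** **Inputs.** Two pre-dose sets of three tracings each (Table 11 footnote p; Protocol 7.4.2.5; SAP 3.4.2.3) and the above-30 and above-60 msec limits (SAP 4.6.5.2). The documents give no QTc error SD and no figure to reproduce. So *s*, the error SD of one triplicate-set mean, and *ρ*, the error correlation between the two pre-dose sets, are assumptions, shown over a range. The post-dose set's error is taken as independent of both pre-dose sets, all sets have equal SD, and errors are normal.

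**Step 1: SD of a change from baseline.**
- Later set only: s√(1 + 1) = s√2.
- Mean of both sets: s√(1 + (1 + ρ)/2).
- Ratio: √[(1 + (1 + ρ)/2)/2].

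| ρ | Ratio | Fall in SD |
|---|---|---|
| 0 | 0.866 | 13.4% |
| 0.25 | 0.901 | 9.9% |
| 0.5 | 0.935 | 6.5% |
| 0.75 | 0.968 | 3.2% |

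At ρ = 1 the ratio is 1. With equal set SDs, averaging never raises the variance.

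**Step 2: false above-30 rate per post-dose set, no true change.** P(Z > 30/SD of change):

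| s (msec) | Later set only | Both sets, ρ = 0 | Both sets, ρ = 0.5 |
|---|---|---|---|
| 7 | 0.12% | 0.02% | 0.06% |
| 10 | 1.70% | 0.72% | 1.17% |
| 12 | 3.86% | 2.06% | 2.94% |

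For s = 10 the three SDs are 14.14, 12.25 and 13.23 msec. At s = 5 the rate is about 0.001% even under the current rule.

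**Step 3: missed changes.** For a true 40 msec increase at s = 10, the chance that a set exceeds 30 msec is Φ(10/14.14) = 76% with the later set only. With both sets it is Φ(10/12.25) = 79% at ρ = 0, or Φ(10/13.23) = 78% at ρ = 0.5.

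**Step 4: per patient, dose levels 1-7.** There are five post-dose sets: 1, 2, 4 and 6 hours, and End of Treatment. By simulation of 1,000,000 patients at ρ = 0, the chance of at least one false above-30 change falls from 6.4% to 3.2% at s = 10, and from 13.3% to 8.7% at s = 12. At s = 10 the drop is 3.2 points, or 3 × 0.032 = 0.10 to 6 × 0.032 = 0.19 patients per regimen of 3 to 6.

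**Step 5: above 60 msec.** Under either rule the false rate per set is at most about 0.02% (s = 12).

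**Step 6: dose levels 8-13.** Under SAP 3.4.2.3 the same calculation applies. Under Protocol 7.4.2.5 as written, no Cycle 1 Day 1 pre-dose set is named. The last value before first dose would then be the screening triplicate, and there would be no second set to average.

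**The case against.** The last value before first dose is a defined, prespecified baseline rule, not an error. No decision rule written in the protocol or SAP uses the change categories. The QTc dose-modification entries in protocol Table 7 use absolute limits, and Protocol 5.6.1 suspends enrollment for Grade 4 QTc prolongation. Protocol 7.4.2.5 bases patient management on the local ECG reading. SAP 4.1.1 makes all reporting descriptive. All of this stands, and it keeps the point minor.

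The size is also open to challenge. Two sets taken within the same hour may well have correlated errors, so the independent case is the best case. The 17 to 33 point swing describes what one misclassified patient does, not how often it happens. Step 4 puts the avoided misclassification at 0.1 to 0.2 patients per regimen even with independent errors.

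Three stronger readings are tempting, and the documents do not support them:
- **That every regimen loses a set.** Protocol 7.4.2.5 names no Cycle 1 Day 1 pre-dose pair for dose levels 8-13.
- **That the earlier set is discarded.** SAP 4.1.1 and 4.1.2 send all data to patient listings; it is only left out of the baseline.
- **That the above-60 or absolute QTc results are compromised.** The above-60 effect is negligible, and the absolute categories do not use baseline.

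It is also an inference, though a reasonable one, that the last value means the last triplicate mean. SAP 4.1.4 does not say so; the within-set averaging in SAP 4.6.5.2 points that way. If it were read as the last single tracing, the loss would be larger.

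**Conclusion.** The point holds for dose levels 1-7: the ECG baseline leaves out half of the pre-dose data collected for it, and change from baseline is noisier than it need be. For dose levels 8-13 it holds under SAP 3.4.2.3 and is unsettled under Protocol 7.4.2.5, so those passages must be reconciled.

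The gain is modest and practically confined to the above-30 category. Its direction needs only equal set SDs and a between-set correlation below 1. Its size rests on the assumed *s* and *ρ*, since the documents give neither. Severity is low: this affects the precision of a descriptive safety table, and the case for acting is that the improvement uses data already collected.

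**What to change.** Add to SAP 4.6.5.2: ECG baseline is the mean of all Cycle 1 Day 1 pre-dose replicates (both triplicate sets where collected, up to 6 ECGs); if no Cycle 1 Day 1 pre-dose ECG exists, it is the mean of the last triplicate set before first dose, that is, screening.

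The fallback is needed because a rule naming only Cycle 1 Day 1 could leave baseline undefined at dose levels 8-13. The sentence also settles that baseline is a mean rather than a single tracing.

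Reconcile SAP 3.4.2.3, Protocol 7.4.2.5 and Table 11 footnote p on the pre-dose ECGs for dose levels 8-13, and state which baseline source applies to those patients.

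The cost is one sentence, a clarification of the ECG schedule text and a small change to the baseline derivation. No new data are needed.

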4.1.5 Standard Calculations

Where appropriate, the calculated study day of each assessment or event will be presented with the assessment or event date on patient data listings, where study day will be determined as:

- The assessment/event date minus the date of first dose of study drug, if the assessment/event date is prior to the date of first dose; and
- The assessment/event date minus the date of first dose of study drug, plus one, if the assessment/event date is on or after the date of first dose.

Other variables requiring calculations will be derived using the following formulas:

- **Days:** A duration between two dates expressed in days will be calculated using the following conventions:
 - Later date – earlier date + 1, if the earlier date is on or after the date of first dose of study drug; or
 - Later date – earlier date, if the earlier date is prior to the date of first dose of study drug.
- **Months:** A duration expressed in months will be calculated by dividing the duration in days by (365.25 / 12).
- **Years:** A duration expressed in years will be calculated by dividing the duration in days by 365.25.
- **Change from Baseline:** Change from baseline will be calculated as the post baseline value minus the baseline value.
- **Percentage Change from Baseline:** Percentage change from baseline will be calculated as the change from baseline divided by the baseline value, multiplied by 100.

4.2 Analysis Sets

The analysis sets are defined as follows:

- Safety Analysis Population: Includes all patients who receive at least one dose of study treatment (nanatinostat, valganciclovir, or pembrolizumab). The Safety Analysis Population will be used for all summaries of safety, demographic, and baseline summaries.
- Full Analysis Set: Includes all patients with measurable disease at baseline who receive at least one dose of nanatinostat and valganciclovir with or without pembrolizumab and who have at least one post-baseline tumor assessment. Patients will be analyzed according to the dosing regimen for which they have been assigned. The Full Analysis Set will be used for summaries of tumor response and survival metrics.

Modified Intent-to-Treat Population: Includes all RM-NPC patients who receive at least one dose of study treatment (nanatinostat, valganciclovir, or pembrolizumab), have a confirmed diagnosis of EBV^+ by central pathology review, met all eligibility criteria, and have baseline (screening) and at least one post-baseline tumor assessment for efficacy.

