3.4 Efficacy and Safety Variables

3.4.1 *Efficacy Variables*

3.4.1.1 *Primary Efficacy Variable*

Tumor responses will be assessed by the Investigator per RECIST v1.1 using MRI or CT scan assessments. For patients receiving pembrolizumab, tumor responses will also be assessed per immunologic RECIST (iRECIST). Tumor imaging will be repeated to confirm disease progression using iRECIST.

The primary efficacy endpoint is ORR, defined as the percentage of patients with a CR or PR as assessed by RECIST v1.1 within the first 26 weeks (6 months) of treatment. The ORR will also be calculated using iRECIST for patients receiving pembrolizumab.

3.4.1.2 *Secondary Efficacy Variables*

Secondary efficacy endpoints include the following:

- Time to response (TTR) – defined as the interval from the start of study drug treatment to the date of first documented CR or PR per RECIST or iRECIST.
- Duration of response (DOR) – defined as the interval of time from the date of first observed CR or PR to the date of documented disease progression or death due to any cause, whichever occurs first. Dates of progression and censoring will be determined as described in [Section 4.5.5.2](#);
- Disease control rate (DCR) – defined as the percentage of patients having a CR, PR, or stable disease (SD) at any time during treatment;
- Progression-free survival (PFS) – defined as the interval of time from the start of study drug treatment to the date of first documented disease progression, initiation of new antineoplastic therapy, withdrawal of consent, loss to follow-up, or death due to any cause, whichever occurs first. Dates of progression and censoring will be determined as described in [Section 4.5.5.2](#); and
- Overall survival (OS) – defined as the interval of time from the start of study drug treatment to the date of death due to any cause. Patients without

documentation of death at the time of analysis will be censored at the date the patient was last known to be alive.

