4.5.3 Primary Efficacy Endpoint Analysis Methods

Counts and percentages for each tumor response category assessed by the Investigator per RECIST v1.1 will be presented by dosing regimen. Separate summaries will also be produced by prior anti-PD-1 treatment exposure. Non-evaluable patients are considered non-responders and will be included in the denominator. ORR estimates, from the first post-baseline assessment, with corresponding binomial 95% confidence intervals using the Clopper-Pearson Exact method will also be presented.

For patients receiving pembrolizumab, the analysis will be repeated using iRECIST.

Results from tumor assessments will be provided in separate listings.

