4.5.4 Secondary Efficacy Endpoint Analysis Methods

Disease control rate will be analyzed using the same statistical methodologies as applied to the primary efficacy endpoint in [Section 4.5.3](#).

Duration of response, PFS, and OS will be summarized in days using Kaplan-Meier methodology. The number of patients who experienced the event of interest and the number of patients censored will be presented, as will Kaplan-Meier product limit estimates of the 25th, 50th (median), and 75th percentiles with associated CIs (where estimable) using Greenwood's formula. The range for all patients, as well as those who experience the event of interest will also be summarized. Kaplan-Meier estimates of the survival distribution function over time will be generated for all patients receiving study treatment. The PFS and OS at 12 months (56 weeks) with associated 95% CIs will also be presented.

All derived efficacy measures will also be provided in a separate listing.

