4.5.5.2 Handling of Dropouts or Missing Data

Objective response rate and disease control rate are based on those patients with available data (baseline and post-baseline response assessment). Non-evaluable patients are considered non-responders and will be included in the denominator. The analysis of PFS and DOR will be right-censored according to the conventions described in [Table 2](#). These conventions are based on the FDA Guidance for Industry *Clinical Trial Endpoints for the Approval of Cancer Drugs and Biologics* ([2018](#)) and *Clinical*

Trial Endpoints for the Approval of Non-Small Cell Lung Cancer Drugs and Biologics (2015).

Table 2 Conventions for Censoring for DOR and PFS

Situation	Date of Progression or Censoring	Outcome
No baseline tumor assessments	Randomization (if applicable), or enrollment	Censored
New anti-cancer treatment started before documentation of PD or death	Date of last disease assessment without documentation of PD before start of new treatment	Censored
Death or progressive disease (PD) immediately after more than one consecutively missed disease assessment visit	Date of last disease assessment visit without documentation of PD that is before the first missed visit	Censored
Alive and without PD documentation	Date of last disease assessment	Censored
Treatment discontinuation for undocumented progression, toxicity, or other reason	Date of last disease assessment without documentation of PD	Censored
Death or PD between planned disease assessments	Date of death or first disease assessment showing PD, whichever occurs first	Not Censored
Death or PD after more than one missed visit	Date of last disease assessment without documentation of PD	Censored

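### Both efficacy sets exclude treated patients with no post-baseline scan, so no planned ORR or DCR counts them as non-responders, and the SAP names two different populations for PFS and OS

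*SAP*

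**What the plan says.** For the Full Analysis Set, SAP 4.2 requires measurable baseline disease, and its members must "receive at least one dose of nanatinostat and valganciclovir with or without pembrolizumab and who have at least one post-baseline tumor assessment". It then says: "The Full Analysis Set will be used for summaries of tumor response and survival metrics". Members of the modified Intent-to-Treat (mITT) set must also "have baseline (screening) and at least one post-baseline tumor assessment for efficacy". Protocol 9.3 puts the same condition on both sets.

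SAP 4.5.5.6 makes the Full Analysis Set primary for efficacy and the mITT set the sensitivity population. SAP 4.5.1 names no third efficacy set, and repeats the summaries in the mITT set only if it differs meaningfully.

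On the denominator, SAP 4.5.3 says: "Non-evaluable patients are considered non-responders and will be included in the denominator". SAP 4.5.5.2 repeats that rule, but first states that ORR and DCR "are based on those patients with available data (baseline and post-baseline response assessment"). DCR follows the ORR method (SAP 4.5.4).

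On the time-to-event endpoints, SAP 4.5.4 says: "Kaplan-Meier estimates of the survival distribution function over time will be generated for all patients receiving study treatment".

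SAP 4.8 adds ORR as a primary efficacy endpoint for Phase 1b and records that Phase 2 did not take place.

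**The concern.** Whether a patient is scanned after baseline can depend on outcome. Someone who dies or withdraws early is a treatment failure, yet the set definition removes that patient from numerator and denominator together. The error runs one way: ORR and DCR rise, or stay at zero if nobody responds. The planned sensitivity analysis cannot show the problem, because the mITT set shares the condition.

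Phase 1b is the only part to be analysed, ORR is now primary there, and results are shown by dosing regimen in planned cohorts of 3 to 6, where one missing patient changes the rate visibly.

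For survival, the two SAP sentences can lead two programmers to different curves. Under SAP 4.2, a patient who dies before any scan disappears from OS, an endpoint that needs no scan.

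**Working it through.** **Step 1: who is left out.** The first scheduled scan is at Week 8. Many patients who stop earlier still enter the set through the end-of-treatment (EOT) scan. Those left out are mainly patients who die, withdraw, are lost, or have no EOT scan.

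Protocol 7.4.1.2 waives the EOT scan if the previous scan was within 4 weeks, whatever the reason for stopping. Footnote o of the Schedule of Events states the waiver only for relapse or progression. Protocol 7.2.5 allows a baseline scan up to 21 days before Cycle 1 Day 1. If that scan counts as the previous one, then under 7.4.1.2 (there is no Day 0):

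- baseline scan on Day −21, plus 28 days: EOT visits up to Day 8 need no scan;
- baseline scan on Day −1, plus 28 days: EOT visits up to Day 28 need no scan.

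Protocol 5.5.2 foresees patients who stop early in the DLT window for reasons other than toxicity. They may be replaced, but they remain treated patients. Later follow-up scans could bring some in, but SAP 4.8 moved patients then in Long-Term Follow-Up to End of Study.

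**Step 2: what the non-evaluable rule covers.** Inside the set it has content: a response rated not evaluable, or stable disease followed by loss to follow-up (Protocol Appendix 3, Best Overall Response). A never-scanned patient is outside both sets and outside the available-data limit in SAP 4.5.5.2, so the rule does not apply. This is a tension between the rule and the set definition, not a flat contradiction.

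**Step 3: size for response.** The plan gives no figure for unscanned patients, so there is none to reproduce, and d below is an assumption. With x responders among N treated, the planned estimate is x/(N−d) in place of x/N, a factor of N/(N−d). Intervals are Clopper-Pearson 95%, the SAP's method.

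| Treated N | Responders | d | All treated | Scanned only | Factor |
|---|---|---|---|---|---|
| 3 | 1 | 1 | 33.3% (0.8–90.6) | 1/2 = 50.0% (1.3–98.7) | 1.500 |
| 6 | 1 | 1 | 16.7% (0.4–64.1) | 1/5 = 20.0% (0.5–71.6) | 1.200 |
| 30 | 7 | 1 | 23.3% (9.9–42.3) | 7/29 = 24.1% (10.3–43.5) | 1.034 |
| 30 | 7 | 2 | 23.3% | 7/28 = 25.0% (10.7–44.9) | 1.071 |
| 30 | 7 | 3 | 23.3% | 7/27 = 25.9% (11.1–46.3) | 1.111 |

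The planned Phase 1b total is 27 to 60. At N = 60 the factor is 60/59 = 1.017 for d = 1 and 60/57 = 1.053 for d = 3. The same factor applies to DCR: 14 of 27 with disease control is 51.9%; with 5 unscanned it becomes 14/22 = 63.6%.

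**Step 4: size for survival.** Only unscanned deaths matter. Suppose 15 of 30 treated patients are alive at 12 months, with no other censoring (50.0%). Removing 1, 2 or 3 early deaths gives 15/29 = 51.7%, 15/28 = 53.6% or 15/27 = 55.6%. For PFS, an unscanned patient who leaves alive adds almost no follow-up, so again only unscanned deaths count. SAP Table 2 also censors deaths that follow more than one missed assessment, which narrows this to early deaths.

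**The case against.** The strongest reply is that a response-evaluable set, defined alike in protocol and SAP, is a legitimate prespecified choice. Redefining the primary set after open-label Phase 1b enrolment has ended could itself look post hoc, and an added all-treated sensitivity analysis might be enough. The timing point is fair and is why the change must be recorded. But the change can only lower the response rates or leave them as they are, so it does not invite suspicion of favouring the drug. An extra row alone would leave the primary rate conditioned on survival to a scan.

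On survival, SAP 4.5.1 refers to Section 4.2 for efficacy populations, and the Kaplan-Meier sentence in 4.5.4 is loose: for DOR it cannot mean all treated patients, since only responders have a DOR. It might be read as a curve pooled over regimens. Yet the reference to 4.2 only repeats one side of the conflict. Table 2 also has a censoring rule for patients with no baseline tumor assessment, who could not belong to a set requiring measurable disease at baseline.

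The consequence is limited, and this stands. No formal comparison is planned, the intervals in single cohorts are very wide either way, and Phase 2 will not follow. The number unscanned is unknown, the EOT-waiver route depends on a conditional reading, and the 12-month OS example ignores the administrative censoring that early closure will cause. SAP 4.3.1 and 4.5.1 will show set counts and list each excluded patient with the reason. That discloses the loss; it does not correct the reported rate.

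**Conclusion.** The concern holds. Followed as written, the plan has no ORR or DCR in which a never-scanned treated patient counts as a non-responder, and it specifies the PFS and OS population inconsistently. These points rest on the text alone. The size rests on an assumed d: a few tenths of a point to under 3 points of ORR in the 30-patient example with one to three unscanned, about 3 points in a cohort of 6 and about 17 points in a cohort of 3 with one unscanned and one responder. Because results are descriptive and exclusions are disclosed, this is something to fix before the analysis is run, not a fatal flaw.

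**What to change.** 1. In SAP 4.2, define the Full Analysis Set as all treated patients with measurable disease at baseline. Remove the post-baseline-assessment condition, and state that patients without such an assessment are non-responders for ORR and DCR.
2. Analyse PFS and OS in all treated patients from first dose, and align SAP 4.2 with 4.5.4.
3. Keep the scan-based set as a response-evaluable sensitivity analysis.
4. Delete the available-data sentence in SAP 4.5.5.2.
5. As a separate wording point, SAP 4.5.3 refers to "ORR estimates, from the first post-baseline assessment", while SAP 3.4.1.1 defines the endpoint "as assessed by RECIST v1.1 within the first 26 weeks (6 months) of treatment". Replace the former with best overall response through Week 26.
6. Report, by dosing regimen, how many treated patients had no post-baseline assessment and why.
7. Record the departure from Protocol 9.3 in SAP 4.8.

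The cost is SAP wording and one entry in 4.8. No new data are needed. The response estimates may be slightly less favourable.
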